At the time of enrollment, detailed patient characteristics and baseline laboratory values will be obtained from the electronic medical record. All patients will have the following laboratory values drawn at baseline (if not already available) and clinicians will have the results readily available: complete blood count (CBC) and complete metabolic panel (CMP) as part of routine patient monitoring. During days 1-7 and 8-14 the lowest hemoglobin, Hematocrit will be collected during each interval. During days 1-7 and 8-14 the highest bilirubin and triglycerides will be collected during each interval. All PT/INR values will be collected during the study.

Surrogate markers of device thrombosis such as lactate dehydrogenase values, haptoglobin values, and device power will also be collected.

Any other operations during the study interval will be recorded as well as the details associate with the operation.

Any endoscopies or evaluations to identify gastrointestinal bleeding, neurologic events, or major bleeding will be recorded.

Additionally, blood will be drawn at randomization, day 2 of heparin, day 4 of heparin, day 8 of heparin and day 12 of heparin (5mL of blood per specimen, with maximum of 25mL). These specimens will only be collected if patient has not completed the intervention (e.g. has not bridged to warfarin). This specimen will be frozen for later analysis to further interrogate the hemostatic system. Thrombin generation will be assessed with the use of a functional thrombin generation assay (TGA) (Technothrombin) on the frozen specimen.

Data Management

A database for this study will be created using REDCap (Research Electronic Data Capture). REDCap uses browser-based software for managing research data. We will have access to REDCap through the Division of Biostatistics and Informatics at Washington University. REDCap servers are securely housed and managed by the Division of Biostatistics. All REDCap data transmission is encrypted following the HIPAA-Security guidelines. Patient safety in this study will be addressed with a comprehensive data safety and monitoring plan that complies with National Institutes of Health guidelines. We plan to produce detailed standard operating procedures for all members of the research team. We also plan to train all members of the research team to take proactive steps to minimize the risk for missing data. Protected health information will only be shared with the research team members

G References

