There is much still to be learned in the understanding of bleeding and thrombosis in the perioperative period. Perioperative events can lead to a great deal of variability in pro- and anti-thrombotic hemostatic factor levels.²⁹ Therefore, the propensity for thrombosis and bleeding in individual patients is frequently unpredictable and, can change substantially over time. Opportunity for discovery is heightened for patients with LVADs, given the dearth of rigorous investigations and the unique features of the human-machine interface. With the recent reports of increasing suspected and confirmed devastating (LVAD) pump thrombosis in the early post-implant period⁴, analyses of treatment-related factors such as the method of monitoring anticoagulation are urgently needed. Recent studies in patients with LVADs have correlated factors such as international normalized ratio (INR) in the outpatient setting³⁰, medication use³¹, and elevated systolic blood pressure³² to pump thrombosis and stroke. However, the impact of monitoring IV UFH therapy with aPTT or anti-Xa in the perioperative period on pump thrombosis, stroke and bleeding remains unknown. The early risk for both bleeding and thrombosis in patients with LVADs underlines the urgency of resolving how best to monitor and achieve appropriate anticoagulation with heparin. Given the ongoing challenges with these competing complications, studying the problem in earnest, while taking into consideration perioperative events, is crucial. Clarifying which of these two monitoring approaches is superior will facilitate safer and more effective anticoagulation with heparin in patients with LVADs.

B Study Objectives

Primary Outcome:

Demonstrate the feasibility and success of implementing nomograms for heparin administration based on both aPTT measurement and anti-factor Xa activity.

Feasibility will be determined by: 1) Questionnaires evaluating the practicality and acceptability of the nomograms 2) The percentage of correct dosing adjustments made by the nursing team required to achieve first therapeutic anticoagulation according to the specified directions provided.

Success will be determined by 1) number of dosing changes required to achieve first therapeutic anticoagulation 2) time (in hours) until achievement of first therapeutic anticoagulation 3) percentage of time therapeutic anticoagulation remains after it is achieved

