“Therapeutic anticoagulation” is defined as two consecutive monitoring values within the goal range, according to assigned monitoring assay. (either two consecutive aPTT values within 60-94 seconds or two consecutive anti-Xa values within 0.3-0.7 IU/ml)

Secondary Outcomes:

Explore heparin dosing and the concordance between the aPTT and anti-factor Xa activity in this patient population.

“Concordance” is defined when simultaneously drawn aPTT values and anti-Xas values are within the goal range (aPTT within 60-94 seconds and anti-Xa within 0.3-0.7 IU/ml).

Explore clinical outcomes including pump thrombosis, gastrointestinal bleeding, neurological events such as stroke, and major bleeding in this patient population.

C Study Design

Study setting and design

VAD AntiX feasibility study will take place at Barnes-Jewish Hospital, an academic hospital in affiliation with Washington University Medical Center located in the United States. This trial has been designed in accordance with the SPIRIT (Standard Protocol Items: Recommendations for Interventional Trials) checklist³³. The VAD AntiX feasibility study will be a stratified randomized, trial with one specific aim: (1) Demonstrate the feasibility of implementing nomograms for heparin administration based on aPTT measurement as well as anti-Xa activity. This feasibility trial will be the foundation for a larger pilot trial and subsequent comparative effectiveness trial that will seek to determine the optimal monitoring method of IV UFH in the perioperative period for LVAD patients.

A heparin nomogram is a tool or table used to standardized heparin administration and dosing when heparin is administered as a continuous infusion. Dosing adjustments are prescribed in the table based on the laboratory results.

Subject Selection

All patients 18 and older undergoing HeartMate II®, HeartMate III® or HeartWare®, LVAD implantation at Barnes-Jewish Hospital, St. Louis, Missouri, USA will be eligible for enrollment in this study. This hospital is an academic medical center affiliated with Washington University School of Medicine. Patients will be recruited preoperatively and will provide written informed consent. Any patient who is unable to receive heparin [e.g. patients with heparin-induced thrombocytopenia (HIT)] or an anaphylactic allergy to heparin] will be excluded. Patients who develop HIT during the course of the study will remain enrolled and be included in the intention-to-treat analysis.

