Inclusion criteria:

All patients 18 years of age and older who are undergoing HeartMate II®, HeartMate III® or, HeartWare® LVAD implantation at Barnes Jewish Hospital, St. Louis, Missouri, USA. Legally acceptable representatives will be able to consent for trial participation.

Exclusion criteria:

Any patient who is unable to receive heparin [e.g. patients with heparin-induced thrombocytopenia (HIT)] or an anaphylactic allergy to heparin] will be excluded. Patients who develop HIT during the course of the study will remain enrolled and be included in the intention-to-treat analysis. Additional exclusions include less than 18 years of age, patients with a known hypercoagulable disorder (factor V Leiden, Antithrombin deficiency, Protein C deficiency, Protein S deficiency, Antiphospholipid antibodies, or other thrombophilia), prisoners, pregnant or lactating women. Also, excluded are patients that are recipients of additional mechanical circulatory support (including extracorporeal membrane oxygenation support, right ventricular assist device, and/or impella) during the index LVAD implantation through the end of the study period.

Recruitment and consent:

Patients will be enrolled during a preoperative clinic visit at our Center for Preoperative Assessment and Planning, from the hospital ward at Barnes-Jewish Hospital, St. Louis, Missouri prior to surgery, or a pre-operative visit at the Ventricular Assist Device Surgery Clinic. Formal consent will be obtained from all participants prior to enrollment in the study. Authorized surrogates will be able to consent for trial participation. Any subject will be free to withdraw their consent at any time.

Interventions

Patients will be randomized to either anti-Xa or aPTT nomograms when the decision is made to start anticoagulation. Patients that receive an additional pumping support device during the index surgery, but prior to randomization will be withdrawn from the study and their baseline data will be discarded. In the rare event the patient receives the assistive pumping device after the index surgery and randomization, they will be withdrawn from the study and the data collected up to that point will be retained for analysis. Consistent with our current heparin management strategy, patients in both arms will be started on a fixed heparin dose (e.g. 750units/hour) on the morning of the first post-operative day. On the second post-operative day, patients will be placed on a

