aPTT monitoring group: While on fixed-dose heparin (750 units/hr), an aPTT and an anti-Xa will be sent every 6 hours from the same tube (2.7 ml of blood in a light blue top tube). The tube will be sent and processed via standard procedure for the aPTT assay to which the patient is randomized. A paper requisition form and an assigned study ID number will accompany the tube with an order for an anti-Xa that will result in a research profile blinded to the clinical team, but available to the research team. This will be the process for all the subsequent aPTT/anti-Xa lab draws in the aPTT monitoring group. When the clinical team decides to start weight-based heparin dosing, the aPTT heparin nomogram order bundle will be ordered as per standard of care. The process noted above for lab draws and paper requisition forms will apply to the weight-based heparin nomogram as well. The aPTT and anti-Xa will be drawn every 6 hours until two values are in the therapeutic range. Once two values are within the therapeutic range, they will be drawn every 24 hours. All timed lab draws are current standard of care for patients being monitoring on heparin nomograms at BJH.

anti-Xa monitoring group: While on fixed-dose heparin (750 units/hr), an anti-Xa and an aPTT will sent every 6 hours from one tube (2.7 ml of blood in a light blue top tube). Monitoring heparin therapy with this frequency is current standard of care. The tube will be sent and processed via standard procedure for the anti-Xa assay to which the patient is randomized. A paper requisition form and an assigned study ID number will accompany the tube with an order for an aPTT that will result in a research profile blinded to the clinical team, but available to the research team. This will be the process for all the subsequent aPTT/anti-Xa lab draws in the anti-Xa monitoring group. When the clinical team decides to start weight-based heparin dosing (per standard of care), the anti-Xa heparin nomogram order bundle will be ordered. The process noted above for lab draws and paper requisition forms, will apply to the weight-based heparin nomogram

as well. The aPTT and anti-Xa will be drawn every 6 hours until two values are in the therapeutic range. Once two values are within the therapeutic range, they will be drawn every 24 hours. All timed lab draws are current standard of care for patients being monitoring on heparin nomograms at BJH.

Outcomes data

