For feasibility, questionnaires completed by the nursing staff evaluating the practicality and acceptability of the nomograms will be analyzed with descriptive statistics and compared between the two groups using a Chi square test. The percentage of correct dosing adjustments made by the nursing team required to achieve first therapeutic anticoagulation will be compared between the two groups using a Mann Whitney U test. For success, the number of dosing changes required to achieve first therapeutic

anticoagulation, the time (in hours) to achievement of first therapeutic anticoagulation, and the percentage time therapeutic anticoagulation remains after it is achieved will be compared between the two groups using a Student's t-test if data is normally distributed or a Mann-Whitney U test if data is not normally distributed.

If possible based on population size, concordance between groups of aPTT and anti-factor Xa activity will be assessed with a suitable (parametric or non-parametric) mixed effects statistical model. This approach is likely to yield more accurate information than crude correlation assessments that have been used in other studies, which have not taken into account repeated measures within patients. We will use repeated measures ANOVA and Tukey's test for multiple comparisons to analyze heparin administration in the two groups. With a mixed effects model, we will compare heparin dose in the two groups, while controlling for confounders, including the effect of time on the dose of heparin administered, and assuming an autoregressive covariance structure (the nature of the correlations between measurements for the same patient), as well as a random intercept to allow for some of the effect of potential unknown confounders.

If possible based on study size, markers of gastrointestinal bleeding, major bleeding, neurologic events, and thrombotic complications will be compared with a Chi-square test. Additionally, as able, adjusted logistic regression will be used to explore risk factors for complications. We will use intent-to-treat approach in our analyses. We will also use appropriate imputation methods and test the sensitivity of our results. No imputation is planned for missing primary outcomes data.

F Data Handling and Record Keeping

Data Collection and Methods

All questionnaire's performed will be collected and responses recorded.

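### Time to first therapeutic anticoagulation has no stated time zero, and values drawn on the common fixed heparin dose can satisfy the event before either nomogram is used

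*Combined protocol and SAP*

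**What the plan says.** Section B (Primary Outcome) lists three success measures: the number of dosing changes needed to reach first therapeutic anticoagulation, "time (in hours) until achievement of first therapeutic anticoagulation", and "percentage of time therapeutic anticoagulation remains after it is achieved". A feasibility measure, the percentage of correct nursing adjustments, is also counted up to first therapeutic anticoagulation. The Statistical Plan (section E) repeats "the time (in hours) to achievement of first therapeutic anticoagulation" and names a test. Neither section, nor the Synopsis, gives a time zero.

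Section B says that therapeutic anticoagulation "is defined as two consecutive monitoring values within the goal range, according to assigned monitoring assay". It sets no condition on the phase of treatment in which the values are drawn.

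Section C (Interventions) says that "patients in both arms will be started on a fixed heparin dose (e.g. 750units/hour) on the morning of the first post-operative day". Section D (Nomogram intervention procedure) adds, for the aPTT group, "While on fixed-dose heparin (750 units/hr), an aPTT and an anti-Xa will be sent every 6 hours from the same tube". A parallel sentence covers the anti-Xa group. In each group the tube is processed for the assay to which the patient was randomised, and the other result is hidden from the clinical team.

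The nomogram start is described in two ways. Section C says "On the second post-operative day, patients will be placed on a" weight-based nomogram. Section D says "When the clinical team decides to start weight-based heparin dosing, the aPTT heparin nomogram order bundle will be ordered", with matching text for the anti-Xa group.

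**The concern.** The primary objective is to show that the two nomograms can be implemented and that they succeed. A success measure should therefore record what happens once a nomogram is directing the infusion. As defined, the event can be met by two fixed-dose values, or by one fixed-dose value followed by one nomogram value.

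For a patient who meets it on the fixed dose alone:

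- the number of dosing changes is zero, although no nomogram was used;
- the correct-adjustment percentage is 0/0, and the Statistical Plan rules out imputing missing primary outcomes;
- the percentage-of-time measure begins in the fixed-dose phase and runs through the later switch to weight-based dosing;
- the hours to the event depend on whichever start the analyst picks: ICU arrival, randomisation, fixed-dose start or nomogram start.

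The fixed dose is common to both arms, but the yardstick is not. Early achievement is judged by aPTT in one arm and anti-Xa in the other, and section A (Previous Research and Preliminary Data) reports that the two disagree in LVAD patients at this centre, with a crude correlation of 0.44. One arm could thus show more early achievers without any nomogram action. With 10 patients per arm, two or three such patients would be visible in the results, and this trial is meant to be the foundation for larger ones.

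**Working it through.** The plan has no figure to reproduce: the sample of 20 is one of convenience and no power analysis is planned. The definitional point rests on reading the sections together; the arithmetic only illustrates its possible size.

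**Does the definition admit fixed-dose values?**

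1. The event needs an assigned assay. Section C places randomisation either when the decision to anticoagulate is made or within 12 hours of ICU arrival. Section D describes the fixed-dose draws separately by randomised group. The assigned assay therefore exists in the fixed-dose phase.
2. The event needs consecutive monitoring values. Section D supplies one every 6 hours on the fixed dose and, for the anti-Xa group, describes this as monitoring of heparin therapy.
3. Nothing in sections B or E excludes these values.

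**How many patients could qualify early?**

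Inputs: from the morning of post-operative day 1 to day 2 is about 24 hours, so 24 / 6 = 4 draws. The chance p that a fixed-dose value is in range is not in the documents; 10%, 20% and 30% are assumed. For four independent draws, the chance of at least one consecutive pair in range is

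P = 3p² − 2p³.

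- p = 0.1: 0.030 − 0.002 = 0.028
- p = 0.2: 0.120 − 0.016 = 0.104
- p = 0.3: 0.270 − 0.054 = 0.216

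The expected number of patients is 20P, and the chance of at least one among 20 is 1 − (1 − P)^20.

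| Assumed p | P, 4 draws | Expected of 20 | At least one of 20 |
|---|---|---|---|
| 10% | 2.8% | 0.6 | 43% |
| 20% | 10.4% | 2.1 | 89% |
| 30% | 21.6% | 4.3 | 99% |

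**Sensitivity to the assumptions**

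- *More draws.* If the nomogram started later and eight draws were taken, P would be 6.3%, 22.1% and 42.2%. These come from the recursion a ← (a + b)(1 − p), b ← a·p, using the previous a and b on the right-hand side, starting at a = 1, b = 0, with P = 1 − a − b after eight steps.
- *Correlated draws.* Successive values in one patient are unlikely to be independent. With a correlation of 0.5 between neighbouring draws (two-state chain), the chance of being in range after an in-range value is c = p + 0.5(1 − p) = 0.55, 0.60 or 0.65, and P = 3pc − 2pc² = 10%, 22% or 33%.
- *Plausible level of p.* 750 / 12 = 62.5, so the fixed rate equals the nomogram's starting rate of 12 units/kg/hour at 62.5 kg and is lower for heavier patients (750 / 80 = 9.4 units/kg/hour at 80 kg). Low values of p must therefore be kept in the range.

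**Does it cancel between arms?**

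A constant offset does, for a difference in hours: 12 v 24 hours becomes 36 v 48 after adding 24 to both, and the difference stays 12 (the ratio moves from 0.50 to 0.75). Early achievement need not cancel. If p were 20% on one assay and 30% on the other, about 10 × 0.104 = 1.0 v 10 × 0.216 = 2.2 patients per arm would qualify before any nomogram action.

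**The case against.** The nomogram-only reading has support. The Synopsis, under Measurements, speaks of both assays being obtained while the patient is on the nomogram or intervention. The objective concerns implementing nomograms, and the two-value rule also appears as a sampling instruction inside both nomogram tables. On this view the team already intends to count only nomogram values, and only the wording is loose. This stands as evidence of intent. It does not limit the definition in section B, and an analyst working from that definition could include fixed-dose values.

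The two descriptions of the nomogram start can be read together, with post-operative day 2 as the schedule and section D as the ordering step. A reader might infer that clinicians who know the arm will delay the start differently by arm. The documents contain no figure showing that start times vary or differ, so this is only a possibility.

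The size rests entirely on assumed in-range chances. At 10% per draw, fewer than one patient in 20 is expected to qualify early. That is correct, and it is why the range is shown.

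Finally, starting the clock at the nomogram uses a post-randomisation event, and a randomised patient who never starts the nomogram has no time zero, in tension with the planned intention-to-treat approach. This is a real cost, and the fix has to address it.

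**Conclusion.** The point holds in a limited form. The hours measure has no time zero, and the event rule as written lets a patient reach first therapeutic anticoagulation on the common fixed dose. That affects the correct-adjustment percentage and all three success measures, and it can differ by arm because the assays differ. With four independent draws and an assumed 10% to 30% chance per draw, about 3% to 22% of patients (0.6 to 4 of 20) would qualify early. Positive correlation between draws or a longer fixed-dose phase would raise these figures. The true rate cannot be found from the documents.

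Three stronger readings are not supported:

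- That the measures fail to measure the nomogram. Both arms share the fixed-dose phase, a common offset leaves a difference in hours unchanged, and most patients may still reach the event on the nomogram. The measures can be contaminated, to an unknown extent.
- That every clock-based measure lacks a start. Percentage of time starts at first achievement; its weakness is that it inherits that event.
- That the change from 6-hourly to 24-hourly draws calls for a particular way of computing percentage of time. The plan states no scoring method to fault, and nothing in the documents shows that interpolation would compare the arms better.

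This should be corrected before analysis. It does not call the design into question.

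**What to change.** In sections B and E:

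1. For the correct-adjustment percentage and all three success measures, count only assigned-assay values drawn after the first nomogram-directed infusion, and start the hours clock at that infusion. In the same edit, say which of the two values dates the event.
2. Report time from randomisation to nomogram start, by arm.
3. List, by arm, randomised patients who never start the nomogram.
4. Give time from randomisation to first therapeutic anticoagulation as a sensitivity analysis, using the recorded randomisation time.

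Sections C (post-operative day 2) and D (when the clinical team decides) must be reconciled on when the nomogram starts. Which is right is for the sponsor.

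The cost is protocol and analysis-plan wording. Heparin dosing details and assay results are already to be collected, so the infusion and draw times should be available from ordinary records. There is one small downside: the main clock then starts after randomisation, at a point that clinical decisions may influence. Items 2 to 4 make any imbalance visible but do not remove it.
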